Clinical investigation plan

**C24-750
(EX-MKTG-159)**

A clinical comparison of two multifocal toric soft contact lenses

[figure not shown]
**A clinical evaluation for
CooperVision Inc**

**Principal Investigator
[name]**

March 2024

Contents

Document control	3
Study summary	
Section 1. Overview	6
1.1 Background	6
1.2 Personnel	6
1.3 Study objectives	6
1.4 Study design	6
1.5 Statistical considerations	6
1.6 Risk analysis	7
1.7 Clinical trial registration	7
Section 2. Resources	8
2.1 Subject selection	8
2.2 Subject discontinuation	9
2.3 Safety parameters, adverse events and concurrent illnesses	9
2.4 Study termination	10
2.5 Protocol deviations	10
2.6 Study resources	10
2.7 Study control	11
2.8 Documentation	11
2.9 Data collection and analysis	12
2.10 Study completion	12
2.11 Subject confidentiality	12
2.12 Study monitoring	12
Section 3. Subject management	13
3.1 Visit scheduling	13
3.2 Visit conduct	13
3.3 Monitoring subject compliance	17
Section 4. Study co-ordination	18
4.1 Document processing	18
4.2 Disclosure	18
4.3 Personnel	18

Study summary

This subject-masked bilateral non-dispensing crossover study will compare the clinical performance and subjective acceptance of the Proclear Multifocal Toric and Biofinity Toric Multifocal soft contact lenses.

Up to 40 subjects will be consented with the aim of completing at least 30 subjects. Each subject will attend an initial visit at which the ideal lens specifications for each lens brand will be determined and ordered. At the second visit, all subjects will be fitted with the Proclear Multifocal Toric lens first followed by the Biofinity Toric Multifocal lens. [REDACTED]

[REDACTED]

A study summary is shown in Table 1.

Visit	Procedures
Visit 1	
Informed consent Explanation of study procedures and subject instructions Ocular, medical and contact lens histories
 
[REDACTED]
 
[REDACTED]
 
Inclusion/exclusion criteria confirmed Proclear MFT fitted (from fitting bank) 15 minutes after application:
 
[REDACTED]
 
Determination of ideal contact lens specification Proclear MFT removed and Biofinity TMF applied (from fitting bank) 15 minutes after application:
 
[REDACTED]
 
Determination of ideal contact lens specification Study lenses ordered
 
Changes to general and ocular health and medications
 
[REDACTED]
 
Proclear MFT applied 1 minute after application:
 
[REDACTED]
 
[REDACTED]
 
Lenses removed Biofinity TMF applied
 
[REDACTED]
 
[REDACTED]

Visit 2	

	Lenses removed [REDACTED]	
	Payment processed	

Table 1: Study summary.

Section 1. Overview

1.1 **Background**

This project seeks to compare the clinical performance of the Proclear Multifocal Toric and Biofinity Toric Multifocal soft contact lenses.

1.2 **Personnel**

This work will be conducted at Eurolens Research, The University of Manchester under the general direction of [name] PhD MCOptom FAAO FBCLA. The Principal Investigator for the work is [name] PhD MCOptom FAAO FBCLA.

1.3 **Study objectives**

This study aims to compare the short-term clinical performance of the two study contact lenses.

1.4 **Study design**

This will be a subject-masked, bilateral study, controlled by cross-comparison. Up to 40 subjects will wear the Proclear Multifocal Toric and the Biofinity Toric Multifocal lens in the clinic only, following an initial visit to determine ideal lens specifications.

1.5 **Statistical considerations**

The principal hypothesis to be tested in this work is that subjective scores for the lenses will be substantially equivalent. The primary outcome variable is subjective distance vision.

[REDACTED]
[REDACTED] As such, these will be compared using linear regression models or other parametric methods. [REDACTED]

[REDACTED]
[REDACTED] Deviations from this plan will be discussed in the final report. Deviations may be necessary due to differences between the actual data distribution compared with the anticipated data distribution.

1.5.1 **Missing, unused and spurious data**

The absence of any data will be carefully and critically considered. If appropriate, partial datasets will be included in the final analysis. Any data missing from a subject visit will be outlined in the report by indicating the number of subjects included for each analysis. Data that are unused or considered to be spurious will be detailed and discussed in the report.

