2.7 Study control

This study is controlled by cross-comparison. Subjects will be masked to the two lens types by means of the investigator opening the lens packaging and ensuring that the subject does not see the lens foil details. Masking may be 'broken' if deemed necessary, by the Principal Investigator or Sponsor.

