3.2.2 Informed consent

The subject will be required to sign an informed consent form prior to enrolment (Appendix B) and before any procedures specific to the clinical investigation are performed. A copy of the signed form will be issued to the subject. When the subject has signed the consent form, they are considered to be enrolled on the study.

3.2.3 Visit 1

Subjects should attend wearing their spectacles.

Written consent from the subject will be obtained as detailed in section 3.2.2.

Subjects will be instructed on the following:

1. [REDACTED].
2. Specific study instructions, such as the importance of not using any other contact lens products.
3. General contact lens information such as the management of red eyes.

The following procedures will be performed (any ocular measurement procedures outlined below will be carried out on each eye):

1. Details of the ocular, medical and contact lens-wearing histories of the subject will be noted [REDACTED]
2. [REDACTED].
3. [REDACTED]
4. [REDACTED]
5. [REDACTED]

[REDACTED]

[REDACTED]

[REDACTED]

[REDACTED]

[REDACTED]

[REDACTED]

The presence of any adverse events will be recorded [REDACTED]

6. The investigator will confirm that the subject satisfies all the inclusion and exclusion criteria. Subjects who fail to meet all the criteria at this time will usually be discontinued and replaced. If the investigator deems the ineligibility to be transient (section 3.1.1), this initial visit may be repeated.
7. Using the fitting set, the Proclear Multifocal Toric lens will be applied and allowed to settle for 15 minutes. The closest available lens specification to the subject's prescription will be selected.
8. [REDACTED]
9. The Proclear Multifocal Toric lenses will be removed.
10. Using the fitting set, the Biofinity Toric Multifocal lenses will be applied and allowed to settle for 15 minutes. The closest available lens specification to the subject's prescription will be selected.
11. [REDACTED]
12. The Biofinity Toric Multifocal lenses will be removed.
13. [REDACTED]
14. [REDACTED]
15. The study lenses will be ordered, taking into account the manufacturers fitting guide [REDACTED]
16. The subject will then be notified of expected timelines for lens receipt and will be subsequently contacted to arrange visit 2. Subjects may wear their habitual lenses and/or spectacles between the two visits.

3.2.4 Visit 2

1. Any changes to ocular or general health and medication will be recorded.

2. [REDACTED]

[REDACTED]

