4. The Proclear MFT lenses will be applied and allowed to settle for one minute.

5. [REDACTED]

6. The subject will be allowed to adapt to the lenses away from the consulting room for 15 minutes.

7. After 15 minutes adaptation, the subject will return to the clinic.

8. [REDACTED]

9. [REDACTED]

[REDACTED]

[REDACTED]

10. [REDACTED]

[REDACTED]

11. The subject will be asked to score the following with reference to appropriate vertical visual analogue scales (0-100) [REDACTED]:

- [REDACTED]
- Distance vision
- [REDACTED]
- [REDACTED]

8. The Proclear MFT lenses will be removed.

9. The Biofinity TMF lenses will be applied and allowed to settle for one minute.

10. [REDACTED]

11. The subject will be allowed to adapt to the lenses away from the consulting room for 15 minutes.

12. [REDACTED]

[REDACTED]

[REDACTED]

[REDACTED]

15. The subject will be asked to score the following with reference to appropriate vertical visual analogue scales (0-100) [REDACTED]:

- [REDACTED]
- Distance vision
- [REDACTED]
- [REDACTED]

16. The Biofinity TMF lenses will be removed.

17. [REDACTED]

18. [REDACTED]

20. At the final visit (or when the subject is discontinued at an earlier visit) the subject will either be provided with a cash payment [REDACTED]

[REDACTED] They will then be discharged, although they may have been asked by the investigator to attend a post-study follow-up visit. They should continue to use their lenses (and solutions if applicable) as advised, and seek aftercare for their contact lenses.

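### Every subject wears Proclear first and Biofinity second, so the lens difference cannot be separated from the order effect

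*Combined protocol and SAP*

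**What the plan says.** The Study summary describes the design this way: "This subject-masked bilateral non-dispensing crossover study will compare the clinical performance and subjective acceptance" of the two lenses. For visit 2 it then states that "all subjects will be fitted with the Proclear Multifocal Toric lens first followed by the Biofinity Toric Multifocal lens". Section 1.4 adds "This will be a subject-masked, bilateral study, controlled by cross-comparison", and section 2.7 repeats "This study is controlled by cross-comparison".

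The rest of the plan follows the same single order:

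- Table 1 lists Proclear before Biofinity at both visits.
- Table 2 (section 2.6.1) labels Proclear as the first lens and Biofinity as the second.
- Section 3.2.3 (visit 1) fits Proclear at step 7 and Biofinity at step 10.
- Section 3.2.4 (visit 2) starts with "The Proclear MFT lenses will be applied and allowed to settle for one minute". After the Proclear scores are taken and the lenses removed, it continues with "The Biofinity TMF lenses will be applied and allowed to settle for one minute".

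The principal hypothesis in section 1.5 is that "subjective scores for the lenses will be substantially equivalent", with subjective distance vision as the primary outcome. The visible text has no randomisation, counterbalancing, second sequence or period adjustment.

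**The concern.** A crossover controls for period because different subjects receive the treatments in different orders. With one order, anything that moves the second score relative to the first is counted as a Biofinity effect.

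Such movement is plausible here. The primary outcome is a 0-100 self-rating, given twice at one visit after 15 minutes of adaptation to each lens. Adaptation to multifocal optics, tiredness, practice with the scale and anchoring on the first lens could each shift the second rating. Masking hides the brand from the subject, but not which lens came second.

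The bias can run either way. It can hide a real difference, giving false equivalence, or create an apparent difference between lenses that perform the same. More subjects only narrow the interval around the biased value.

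A smaller point: a subject who stops part-way through visit 2 after giving the first scores will always be missing the Biofinity score.

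**Working it through.** **Inputs.** Section 1.5.2 gives intra-subject SDs of 18 (comfort), 16 (distance vision), 19 (near vision) and 17 (overall), a meaningful difference of 10 units, alpha 0.05, 30 subjects and power of at least 0.80. Order-effect sizes are my assumptions.

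**Reproducing the plan's sample size.** Take the SD as that of the paired difference, a true difference of zero, and two one-sided tests (TOST) at 0.05 each. The normal approximation is n = [SD × (1.645 + 1.282) / 10]². For SD 16, 17, 18 and 19 this gives 21.9, 24.7, 27.7 and 30.9, so 22, 25, 28 and 31. The largest is close to the stated 30, so this reading is used below.

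**Identifiability.** Write τ for Biofinity minus Proclear, π for period 2 minus period 1, and λ for carry-over from the first lens into the second score. With the fixed order, the expected paired difference is τ + π + λ(Proclear). The design matrix for 30 subjects (30 subject columns, one lens, one period) has 32 columns but rank 31, because the lens and period columns are identical. With 15 subjects per order the rank is 32 of 32.

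**Precision.** The standard error is 16/√30 = 2.92. The half-width of the 90% interval is 1.699 × 2.92 = 4.96 units. An order effect of 5 units therefore moves the estimate by a full half-width, about 1.7 standard errors.

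**Probability of declaring equivalence.** This is exact TOST, integrating over the chi-square distribution of the sample variance (n = 30, 29 df, margin ±10). The expected difference is the order effect when the lenses are identical. It is 10 minus the order effect when the lenses truly differ by 10 and the order effect opposes that difference.

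| Order effect (assumed) | Identical lenses, SD 16 | True difference 10, SD 16 | Identical lenses, SD 22.6 | True difference 10, SD 22.6 |
|---|---|---|---|---|
| 0 | 0.91 | 0.05 | 0.53 | 0.05 |
| 3 | 0.75 | 0.26 | 0.43 | 0.17 |
| 5 | 0.51 | 0.51 | 0.29 | 0.29 |
| 8 | 0.16 | 0.84 | 0.12 | 0.48 |

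The SD 22.6 columns cover the other reading of section 1.5.2, in which 16 is the SD of a single measurement and the paired SD is √2 × 16.

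**More subjects.** The same calculation at SD 16 with 40 completers, a true difference of 10 and an opposing order effect of 5 gives false equivalence of 0.62, against 0.51 with 30.

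**Balanced order.** Period 2 minus period 1 has expectation τ + π + λ(Proclear) in one sequence and −τ + π + λ(Biofinity) in the other. Half the difference between the sequence means is τ + [λ(Proclear) − λ(Biofinity)]/2, so π cancels. With 15 per sequence the variance is ¼ × (16²/15 + 16²/15) = 16²/30, the same as before, on 28 df. Without differential carry-over, power is 0.91 and false equivalence 0.05 whatever the order effect. Power for SD 17, 18 and 19 is 0.866, 0.814 and 0.757, against 0.867, 0.815 and 0.758 for the fixed order with no order effect.

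**The case against.** **Balancing is not a complete cure.** If the first lens affects the second score differently depending on which lens it was, a period term does not remove that. The balanced estimate is biased by half the differential carry-over. For an assumed differential of 3, 5 or 8 units (shifts of 1.5, 2.5 or 4), power falls to 0.87, 0.80 or 0.64. False equivalence at a true difference of 10 rises to 0.13, 0.21 or 0.38. This stands as a limit on what the fix delivers. It does not favour the fixed order, which absorbs the carry-over from Proclear and the whole period effect as well.

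**The order effect may be small.** Subjects are current or recent soft-lens wearers (section 2.1.3), have worn both lenses at visit 1, get the same settling and adaptation times at visit 2, and are masked. These features plausibly reduce novelty effects, but they do not make the order effect zero, and this design cannot estimate it. The documents give no order-effect size, and 8 units is close to the whole margin, so the table is illustrative.

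**Redaction.** Text after the fixed-order sentence, in the analysis section and among the visit 2 steps is blacked out. A rationale, rest period or stated limitation may be there, so the choice cannot be called unjustified. A hidden analysis cannot restore identifiability, because that is a property of the design.

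**Secondary points.** Visit 1 sets lens specification, so its order does not have to be randomised to separate lens from period in the visit 2 outcome. The part-way dropout point is minor in one short sitting, and sections 1.5.1 and 2.2 deal with partial data and replacement.

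**Conclusion.** The concern holds, and the design is wrong as written for its stated purpose. Five places in the plan agree on one order, so this is not a slip in one sentence. The lens difference is identifiable only by assuming that the order effect is zero or known, and the principal hypothesis is about the lenses.

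The aliasing itself depends on no numerical assumption. The size does: it rests on 30 completers, SD 16 as the paired SD, a 10-unit margin, TOST at 0.05 and assumed order effects. On that basis even 3 units, less than a third of the margin, takes false equivalence from 0.05 to 0.26 and power from 0.91 to 0.75. Under the larger-SD reading the bias has the same direction, with 3 units taking false equivalence from 0.05 to 0.17. The problem must be fixed before data collection, since it cannot be repaired afterwards.

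**What to change.** - At visit 2, randomise subjects 1:1 to Proclear-then-Biofinity or Biofinity-then-Proclear from a blocked list.
- Analyse with lens and period as fixed effects and subject as a random effect, or by the equivalent two-sequence paired analysis. State that the result assumes no differential carry-over between lenses.
- Rewrite the Study summary, Table 1, the first-lens and second-lens headings of Table 2, and the steps of section 3.2.4 to match. Randomising the fitting order at visit 1 as well is sensible but secondary.
- If the order must stay fixed, remove the crossover label, give the reason, and limit the conclusion to Biofinity worn after Proclear.

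**Cost.** A randomisation list and a small protocol amendment, with ethics committee approval if needed under section 2.5.1. One degree of freedom is lost (29 to 28) and power for the primary outcome stays at 0.91. No subjects, visits, lenses or procedures are added.

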1.5.2 Power analysis

Using data from a previous study with multifocal contact lenses, minimum intra-subject standard deviation values on a 0-100 scale for comfort, distance vision, near vision and overall score were 18, 16, 19 and 17 units, respectively. Assuming a meaningful difference of 10 units and an alpha of 0.05, data from 30 subjects are required to provide power of 0.80 or greater for equivalence testing for these four parameters. To allow for ineligible subjects and discontinuations, up to 40 subjects will be recruited.

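### Does comparing the lens scores by linear regression ignore the pairing and leave equivalence untested?

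*Combined protocol and SAP*

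**What the plan says.** The Study summary describes a crossover in which "all subjects will be fitted with the Proclear Multifocal Toric lens first followed by the Biofinity Toric Multifocal lens". Under Visit 2 (section 3.2.4) each subject rates distance vision on a 0-100 visual analogue scale once with each lens, so the two scores form a pair.

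Section 1.5 gives the principal hypothesis, that "subjective scores for the lenses will be substantially equivalent", and adds: "The primary outcome variable is subjective distance vision". After redacted text it says that "these will be compared using linear regression models or other parametric methods". More redacted text follows. What the word *these* refers to, and the reason for choosing the method, are both hidden.

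Section 1.5.2 sets the sample size. It reports that "minimum intra-subject standard deviation values on a 0-100 scale for comfort, distance vision, near vision and overall score were 18, 16, 19 and 17 units". It continues: "Assuming a meaningful difference of 10 units and an alpha of 0.05", and concludes that "data from 30 subjects are required to provide power of 0.80 or greater for equivalence testing for these four parameters".

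**The concern.** Taken alone, the method sentence invites two worries.

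The first is pairing. Regressing score on lens, with nothing in the model for subject, would treat 30 × 2 = 60 scores as independent. Variation between subjects would then sit in the error term. With positively correlated scores the confidence interval would be too wide, and lenses that are equivalent could fail to be shown so.

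The second is the hypothesis. A regression coefficient with its p-value tests for a difference. If a non-significant coefficient were read as equivalence, an imprecise study would be rewarded.

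Either would matter in a study whose main claim is equivalence and whose sample size assumes within-subject precision.

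**Working it through.** **1. Inputs.** From section 1.5.2: SDs of 18, 16, 19 and 17 for comfort, distance vision, near vision and overall score; a difference of 10 units, read as the equivalence margin; alpha 0.05; 30 subjects; power 0.80. Not in the documents and therefore assumed: a true difference of 0, alpha of 0.05 for each of two one-sided tests (TOST), and the correlation rho between a subject's two scores.

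**2. Reproducing the 30.** Read the SDs as SDs of within-subject differences. For a paired TOST, n = (SD × (z0.95 + z0.90) / 10)², with z0.95 = 1.645 and z0.90 = 1.282. For near vision, (19 × 2.927 / 10)² = 30.9, so 31.

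| Calculation | Comfort | Distance | Near | Overall |
|---|---|---|---|---|
| Paired TOST, normal approximation, n | 28 | 22 | 31 | 25 |
| Paired TOST, exact t, n | 30 | 24 | 33 | 27 |
| Paired TOST, exact power at n = 30 | 0.815 | 0.910 | 0.758 | 0.867 |
| Paired TOST, 0.025 per side, exact n | 37 | 29 | 40 | 33 |
| SDs read as per-measurement (SD of difference = √2 × SD), exact TOST n | 57 | 46 | 64 | 51 |
| Paired two-sided difference test, n | 28 | 23 | 31 | 25 |

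An unpaired equivalence calculation needs 44 to 62 subjects per group for SDs of 16 to 19. The stated 30 therefore fits a paired calculation. It does not by itself separate a paired equivalence test from a paired difference test, because both give 31 for near vision. The wording of section 1.5.2 settles that: it names equivalence testing.

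**3. Can linear regression respect the pairing?** Yes. Fit score on lens plus subject as a factor, with 30 complete pairs. Residual degrees of freedom are 60 − 30 − 1 = 29 and the residual variance estimates SD²/2, where SD is that of the differences. The standard error of the lens effect is √(2 × (SD²/2) / 30) = SD/√30. For distance vision this is 16/√30 = 2.92, the paired t-test standard error on the same 29 degrees of freedom. The confidence interval for that coefficient can be set against −10 and +10, which is an equivalence test.

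**4. What if subject were left out?** With variance s² for each score, SD² = 2s²(1 − rho). The unpaired standard error is s√(2/30) = (SD/√30) / √(1 − rho), so it is inflated by 1/√(1 − rho). Simulated results for distance vision (SD of difference 16, n = 30, TOST at 0.05 per side):

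| Assumed rho | SE inflation | Power, unpaired | Power, paired | Type I error at the margin, unpaired |
|---|---|---|---|---|
| 0 | 1.00 | 0.92 | 0.91 | 0.049 |
| 0.3 | 1.20 | 0.84 | 0.91 | 0.025 |
| 0.5 | 1.41 | 0.70 | 0.91 | 0.011 |
| 0.7 | 1.83 | 0.31 | 0.91 | 0.002 |

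The arithmetic is sound, but it describes an analysis that the documents do not state. Even there the error is conservative: power is lost and false claims of equivalence become rarer.

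**The case for a change.** The strongest case for the concern is that the readable sentence leaves the choice of method open. Some methods it allows match the power calculation; score regressed on lens alone does not. No readable sentence names a subject term, a paired difference or a confidence-interval rule. The 10 units appear only in the power section, as a meaningful difference rather than a decision margin. Section 1.5 also permits departures from the plan if the data are not distributed as expected. An equivalence claim is best protected by fixing the model and the rule before data are seen.

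These observations are accurate, but they show only that the readable text is brief. The model terms and the rule would naturally stand next to the quoted sentence, and that text is redacted, so their absence cannot be charged to the plan. What can be read (a crossover, intra-subject SDs, an equivalence hypothesis, equivalence testing) gives an analyst no reason to drop subject from the model or to take non-significance as proof of equivalence. Writing out the subject term and the interval rule would be tidy, but would correct no demonstrated mistake. A period term could not usefully be added: every subject wears the lenses in the same order, so lens and period are completely aliased.

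**Conclusion.** The concern does not stand. No readable sentence says that subject is omitted, that the 60 scores are treated as independent, or that a non-significant difference will count as equivalence. The method wording is compatible with a paired analysis, and the sample size is close to what a paired equivalence test requires.

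The power losses at correlations of 0.3 to 0.7 depend on an unpaired model that the documents do not describe and on correlations that they do not give. At zero correlation there is no material loss.

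This conclusion has two limits. Agreement with the stated 30 assumes that the quoted SDs are SDs of within-subject differences and that the true difference is zero. Read as per-measurement SDs, 30 subjects would give power of 0.53 for distance vision and 46 would be needed. Exact paired power for near vision at 30 subjects is 0.76, slightly under the stated 0.80, but near vision is not the primary outcome. Neither limit shows that the analysis ignores pairing.
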